6.2 RESPONSE CRITERIA

While the evaluation of the response of KS to an agent or regimen is difficult to grade by means of commonly used oncologic definitions, in an effort to standardize the evaluation of therapy against KS, the AIDS Clinical Trial Group Oncology Committee has devised a set of staging and response definitions for KS. We will use a modification of these criteria to assess responses, which is consistent with the criteria used in our previous KS studies. It should be noted that there is some observer variability in the evaluation of the number, size, nodularity, and color of lesions, and this must be taken into account when measurements are interpreted.

- For the purposes of this study, patients should be evaluated at baseline and re-evaluated for response on day 1 of every cycle or every other cycle depending on study (see sections [6.2.1](#) and [6.2.2](#) below) and at the end of treatment.
- For assessment of response, only patients who complete at least two cycles of therapy are evaluable.
- For evaluation of less than complete responses in subjects with more than 50 lesions at entry, only the previously selected 1 - 3 representative areas that contain at least 20 lesions will be considered. However, complete responses still require the absence of any detectable disease over the entire body (i.e. not confined to the representative areas).

6.2.1 Methods of Evaluation for Measurable Disease

6.2.1.1 KS Tumor Photography

Baseline whole body photographs will be obtained upon entry into the study. At this time, 5 lesions (hereafter called marker lesions), representative of the patient's disease and, if possible, located on separate areas of the body will be selected. These marker lesions should be lesions that have never been treated with local therapies such as radiation therapy or intralesional injections. An attempt will be made to distribute the "marker" lesions between the representative areas (described below in section [6.2.1.3.1](#)) and the rest of the body. Detailed photographs of these lesions will be obtained with a metric rule beside them.

After baseline, photography will be repeated day one of the first six cycles; for any patients receiving more than six cycles, photography will be repeated on alternate cycles (on odd-numbered cycles, starting with cycle 7) thereafter. Photography will also be performed on day 29 of the final cycle.

For subjects receiving a second course of pomalidomide (Section [3.1.6](#)), a new tumor baseline will be determined immediately prior to commencement of the second course as described above. Documentation of extent of disease and response to therapy will follow the same schema described for the initial course of therapy, with all comparisons made against this new baseline.

6.2.1.2 Documentation of Marker Lesions

The size, color and nodularity of the marker lesions will be recorded on Day 1 of each cycle and on day 29 of the final cycle. Documentation will depend on the number of lesions.

6.2.1.3 Documentation of Extent of Disease

6.2.1.3.1 *Subjects with 50 or more KS lesions:* for subjects with 50 or more lesions at entry, between 1 and 3 representative areas will be selected at baseline and these will be used for each subsequent evaluation. Representative areas are sections of the body (e.g. the back, a leg, an arm, etc.), which contain at least 20 KS lesions. The total number of lesions in these representative areas will be counted and a record made of whether they are flat or raised. If, in the course of treatment, a single lesion breaks up into 2 or more smaller lesions whose area does not extend beyond the boundary of the initial lesion, these lesions will still be counted as single lesions for the purpose of assessing total numbers in defining a response to therapy.

After baseline, the number of lesions within the representative areas will be counted at the completion of each cycle.

6.2.1.3.2 *Subjects with fewer than 50 KS lesions:* for subjects with less than 50 lesions at entry, the total number of lesions will be counted and a record made of whether they are flat or raised.

After baseline, the number of lesions within the representative areas will be counted at the completion of each cycle.

6.2.1.3.3 Additional studies for visceral KS involvement: additional studies, including but not limited to, gastrointestinal endoscopy and bronchoscopy will be performed at entry where clinically indicated, based on clinical evaluation of the patient.

6.2.1.4 KS Tumor Non-invasive Imaging

Evaluation of the vascularity in KS will be performed using 3 non-invasive modalities: laser Doppler imaging, multi-spectral imaging, and infrared thermal imaging. Imaging will use the modalities previously explored in study 01-C-0158([144](#), [145](#)). A target lesion of KS as well as normal skin will be identified and recorded for follow-up studies. The target lesion will also be measured and photographed. These are correlative studies performed in parallel with tumor response assessment, and are not considered in the evaluation of KS response by modified ACTG criteria.

After baseline, imaging will be repeated on day one of the first six cycles; and for any patients receiving more than six cycles, imaging will be repeated on alternate cycles (on odd-numbered cycles, starting with cycle 7) thereafter. Imaging will also be performed on day 29 of the final cycle.

For subjects receiving a second course of pomalidomide (Section [3.1.6](#)), a new tumor baseline will be determined immediately prior to commencement of the second course as described above. Documentation of extent of disease and response to therapy will follow the same schema described for the initial course of therapy, with all comparisons made against this new baseline.

6.2.1.5 KS tumor biopsies

See section [5.1.2.3](#)

6.2.2 *Quality of Life Evaluation*

Quality of life assessment will be performed using the Functional Assessment of HIV Questionnaire([153](#)) (see also www.facit.org), adapted with the inclusion of three additional questions directed at specific assessment of KS impact on quality of life developed for a prior AIDS Malignancy Consortium study in KS([85](#)) (

Appendix 6 [English] and **Appendix 7** [Spanish]). The questionnaire will be self-administered by subjects in an environment providing visual and auditory privacy and free from distractions. Questionnaires will be administered at baseline, on day 1 of cycle 4 and 28 days after the completion of the final cycle.

For subjects who are not fluent in English or Spanish, where an approved translated version of the FAHI questionnaire for the patient's first language is available from the Functional Assessment of Chronic Illness Therapy group (www.facit.org/questionnaires) these may be used in place of the questionnaire in

Appendix 6 and **Appendix 7**. Where a suitable questionnaire is not available, the English version may be used *only* with the assistance of an approved translator.

For subjects whose written literacy in the language of FAHI questionnaire administration is questionable, the questionnaire may be administered orally with the verbal and recording assistance of an approved translator or member of the study clinical team.

For subjects receiving a second course of pomalidomide (Section **3.1.6**), a new quality of life baseline will be determined immediately prior to commencement of the second course as described above. Questionnaires will be administered immediately prior to commencement of the second course, on day 1 of cycle 4 of the second course, and 28 days after the completion of the final cycle of the second course. Comparisons will be made to the new baseline.

6.2.3 Response Criteria

Complete Response:

- The absence of any detectable residual disease, including tumor associated edema, persisting for at least 4 weeks.
- For subjects with pigmented macular skin lesions persisting after apparent complete response, a biopsy of at least one representative lesion is required to document the absence of malignant cells. If a lesion has not been biopsied, the patient may be classified as having a clinical CR.
- For subjects with visceral disease, the diagnostic radiologic or endoscopic study should be repeated if not medically contraindicated and found to be negative for evidence of disease. If such procedures are medically contraindicated but the patient has no clinical evidence of visceral disease, the patient may be classified as having a clinical CR.

Clinical Complete Response:

- The absence of any detectable residual disease, including tumor associated edema, persisting for at least 4 weeks.
- For subjects with pigmented macular skin lesions persisting after apparent complete response, if a representative lesion has not been biopsied.

For subjects with visceral disease, the diagnostic radiologic or endoscopic study should be repeated if not medically contraindicated and found to be negative for evidence of disease. If such procedures are medically contraindicated but the patient has no clinical evidence of visceral disease, the patient may be classified as having a clinical CR.

Partial Response

- No progressive disease (see below and noting, that single lesions which split up into 2 or more smaller lesions during the course of treatment will still be counted as one); no new lesions occurring in previously uninvolved areas of the body; no new visceral sites of involvement or the appearance or worsening of tumor-associated edema or effusions and:
- A 50% or greater decrease in the number and/or size of previously existing lesions lasting for at least 4 weeks *or*
- Complete flattening of at least 50% of all previously raised lesions (i.e., 50% of all previously nodular or plaque-like lesions become macular) lasting for at least 4 weeks *or*
- A 50% decrease in radiologically measurable visceral lesions sustained without evidence of re-growth for at least 4 weeks *or*
- A 50% decrease in radiologically measurable visceral lesions sustained without evidence of re-growth for at least 4 weeks *or*
- Subjects who otherwise meet the criteria for a CR but still have residual tumor-associated edema or effusions will be classified as having a PR.

Progressive Disease

- For those criteria that involve measurement of lesions in the clinic, the designation of progression should be made, when feasible, only when the criteria below have been met in two measurements spaced at least 1 week apart. For the assignment of progressive disease for the primary outcome analysis, progression will be defined in comparison to baseline measurements.
- An increase of 25% or more over baseline in the number of lesions and/or the size (sum of the products of the largest perpendicular diameters) of the marker lesions *or*
- A change in character from macular to plaque-like or nodular of at least 25% of the lesions *or*
- New visceral sites of involvement or progression of visceral disease *or*
- The development of new or increasing tumor-associated edema or effusion that lasts at least 1 week and interferes with the patient's normal activities.
- Clarification: There is a certain variability in the measurement of KS lesions, and this becomes particularly problematic if patients have very few lesions. To mitigate against this effect, if the cutaneous burden of KS is at any time 8 or less lesions, progressive disease will require the development of at least 2 new lesions. Similarly, if the cutaneous burden of KS is at any time 8 or less nodular lesions, progressive disease will require the development of at least 2 new nodular lesions.

Stable Disease

- Any tumor measurement not meeting the criteria for Complete Response, Partial Response, or Progressive Disease.

Overall Response

- Overall response rate is the sum of complete responses, clinical complete responses, and partial responses.

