2 ELIGIBILITY ASSESSMENT AND ENROLLMENT

2.1 ELIGIBILITY CRITERIA

2.1.1 *Inclusion Criteria*

- 2.1.1.1 Age \geq 18 Years.
- 2.1.1.2 Any HIV status.
- 2.1.1.3 Kaposi sarcoma pathologically confirmed by Department of Pathology, Clinical Center, National Institutes of Health.
- 2.1.1.4 At least five measurable KS lesions with no previous local radiation, surgical or intralesional cytotoxic therapy that would prevent response assessment for that lesion.
- 2.1.1.5 ECOG Performance Status \leq 2
- 2.1.1.6 Life expectancy \geq 6 months
- 2.1.1.7 For patients with HIV-associated KS:
 - 2.1.1.7.1 Must be receiving, and adherent to, a HAART regimen consistent with current clinical guidelines.
 - 2.1.1.7.2 Must have been receiving HAART for at least one month.
 - 2.1.1.7.3 Must have achieved an HIV VL $<10,000$ copies/mL.
- 2.1.1.8 The following hematological parameters:
 - 2.1.1.8.1 Hemoglobin \geq 10 g/dL
 - 2.1.1.8.2 Platelets \geq 75,000 cells/mm³
 - 2.1.1.8.3 Absolute neutrophil count (ANC) \geq 1000 cells/mm³
- 2.1.1.9 The following biochemical parameters:
 - 2.1.1.9.1 Estimated or measured creatinine clearance \geq 45mL/minute (see [Appendix 9](#) for estimation of creatinine clearance)
 - 2.1.1.9.2 Serum alanine aminotransferase (ALT) \leq 2.5 x upper limit of normal

- 2.1.1.9.3 Serum aspartate aminotransferase (AST) $\leq 2.5 \times$ upper limit of normal
- 2.1.1.9.4 Bilirubin $\leq 1.5 \times$ upper limit of normal unless the patient is receiving protease inhibitor therapy (e.g. indinavir, ritonavir, nelfinavir, or atazanavir) known to be associated with increased bilirubin, in which case total bilirubin $\leq 7.5 \text{ mg/dL}$ with direct fraction $\leq 0.7 \text{ mg/dL}$.

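### The low-burden clarification in Section 6.2.3 does not say which progression criterion it modifies and, read literally, overrides the marker-size, character, visceral and edema criteria

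*Combined protocol and SAP*

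**What the plan says.** Section 6.2.3 of the combined protocol and SAP gives the grounds for PD as a list joined by *or*:

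- count or size: "An increase of 25% or more over baseline in the number of lesions and/or the size" of the marker lesions;
- character: "A change in character from macular to plaque-like or nodular of at least 25% of the lesions";
- visceral: "New visceral sites of involvement or progression of visceral disease";
- new or increasing tumor-related edema or effusion that lasts at least a week and limits activity.

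For the primary outcome analysis, PD is judged against baseline.

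A clarification follows the list. Its reason is: "There is a certain variability in the measurement of KS lesions, and this becomes particularly problematic if patients have very few lesions". Its rule is that "if the cutaneous burden of KS is at any time 8 or less lesions", then "progressive disease will require the development of at least 2 new lesions". A parallel sentence says that with 8 or fewer nodular lesions, "progressive disease will require the development of at least 2 new nodular lesions".

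Four other places bear on the reading:

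- Section 2.1.1.4 sets the entry minimum: "At least five measurable KS lesions with no previous local radiation" or other local treatment that would prevent assessment.
- The partial response (PR) definition in Section 6.2.3 excludes PD. Separately, it excludes new visceral sites, new or worsening edema or effusions, and new lesions in previously uninvolved areas.
- Section 3.6.1.7 (off-therapy) uses the same modified response criteria, sustained for eight weeks, and counts every case of symptomatic visceral disease as clinically significant progression.
- The Appendix 5 flowsheet has separate PR and PD thresholds in three rows: TOTAL, NODULAR and PRODUCT.

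**The concern.** The subject of each sentence in the clarification is progressive disease as a whole, not one item in the list, and nothing says that the other items still apply. An assessor who follows the text as written would need two new lesions before recording PD on any ground. Because the trigger is a low burden at any time, it reaches responders whose counts have fallen as well as subjects who entered with few lesions. The nodular sentence reaches further: a subject with many flat lesions and 8 or fewer nodular ones could not be PD without two new nodular lesions, however far the flat disease spread.

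PD status decides between stable disease (SD) and PD, is one of the bars to PR, and feeds progression-free survival, event-free survival and the off-therapy criterion. Stable disease in a subject who was progressing at baseline is also one of the examples of benefit in Section 3.1.4.2.

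**Working it through.** **1. The plan's own figures.** The Section 10.4 response rules reproduce by the exact binomial tail. P(X ≥ 4 | n = 15) is 0.9095 at 40% and 0.0556 at 10% (plan: 90.9%, 5.6%). P(X ≥ 3 | n = 10) is 0.8327 and 0.0702 (plan: 83.3%, 7.0%). The clarification does not alter these; they matter only for how much one reclassified subject counts.

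**2. What a count floor would change.** Inputs are the 25% threshold, the cut-off of 8 and the floor of 2 (Section 6.2.3), and the entry minimum of 5 (Section 2.1.1.4). The fewest new lesions that meet the 25% rule at a reference count n is ceil(0.25 × n).

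| Reference count n | 0.25 × n | New lesions by 25% rule | With floor of 2 if n ≤ 8 |
|---|---|---|---|
| 1 to 4 | 0.25 to 1.00 | 1 | 2 |
| 5 to 8 | 1.25 to 2.00 | 2 | 2 |
| 9 to 12 | 2.25 to 3.00 | 3 | 3 (not triggered) |

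Read as a floor on the total count against baseline, the first sentence changes nothing, because entry requires at least 5 lesions and 5 to 8 lesions already need two new ones. The floor does act at 1 to 4: on nodular counts, since five measurable lesions may include only a few nodular ones, and on any comparison with a later, lower burden. Appendix 5 leaves a blank for a reference point beside the baseline comparison, so such comparisons are foreseen. The cut-off also fits a count floor, because 25% of 8 is exactly 2.

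**3. What the literal reading would change.** Each example assumes 8 or fewer lesions and fewer than two new ones.

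| Finding | By the list | Clarification read literally | Can the response rate change? |
|---|---|---|---|
| 6 lesions, marker area doubled (+100% against 25%), no PR criterion met | PD | SD | No: neither counts as a response |
| New visceral site | PD | Not PD | No: PR bars it separately |
| New or worsening edema or effusion meeting the PD criterion | PD | Not PD | No: PR bars it separately |
| 6 raised lesions, 3 flattened (50%, held for 4 weeks), marker area doubled | PD, so no PR | PR | Yes |

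Only the last pattern, a PR criterion met alongside marker growth or character change, moves the response rate. One such subject moves it by 1/15 = 6.7 points in the HIV-positive cohort or 1/10 = 10 points in the HIV-negative cohort. The documents do not say how many subjects had 8 or fewer total or nodular lesions, or whether this pattern occurred, so a total effect cannot be computed.

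**4. The text against Section 3.6.1.7.** That section requires PD by these same criteria and also counts all symptomatic visceral disease as clinically significant progression, with no lesion-count condition. For a low-burden subject with a new symptomatic visceral site and no new skin lesions, the literal clarification says there is no PD while Section 3.6.1.7 says there is clinically significant progression. Both cannot hold.

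**The case against.** The strongest case on the other side is that only a count floor was meant. The item is labelled a clarification, and its reason is variability in measuring few lesions, which has nothing to do with visceral disease or edema. Its two sentences match the TOTAL and NODULAR rows of the flowsheet and leave PRODUCT, the marker size, alone. The cut-off of 8 is where 25% equals two lesions. On this view the point is minor wording. The survival endpoints are also buffered: Section 10.4 counts progression only when it requires a change in therapy, and event-free survival also counts death.

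Most of this stands as evidence of intent, and it rules out three stronger inferences.

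- A reader might infer that the clause definitely switches off the other criteria. The purpose sentence and flowsheet point the other way.
- A reader might infer that the literal reading must be right because a count floor would have no work to do. That is true only for the total count against baseline; the floor has work at 1 to 4 nodular lesions or against a later, lower burden.
- A reader might infer that every low-burden subject affected moves the response rate by 6.7 or 10 points. As shown above, most would not move it at all.

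What does not stand is that intent settles the matter. The written rule is unrestricted and contradicts both the list above it and Section 3.6.1.7. The purpose sentence does not clearly spare marker size either: Section 6.2 names size among the features subject to observer variability.

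**Conclusion.** The point holds as one of unresolved scope with a wrong result if the text is followed literally. Once total or nodular lesions number 8 or fewer at any time, the wording makes two new (or new nodular) lesions necessary for any PD. A floor on the two counts was probably intended, but the plan does not say so.

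The exposure is mainly SD recorded in place of PD and later progression dates, the latter damped by the change-in-therapy condition. The response rate is exposed only where a PR criterion coexists with marker growth or character change. One such subject could matter at the thresholds of 3 of 10 or 4 of 15, but the frequency is unknown. Nothing in the documents shows that the clause was applied literally to any subject, so the conclusion rests on the wording alone and does not imply that reported responses are inflated.

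**What to change.** Reword the clarification so that the two-lesion floor applies only to progression judged by the total lesion count (first sentence) or the nodular count (second sentence). State that the visceral and edema/effusion criteria remain sufficient alone. The sponsor should confirm that the marker-size (PRODUCT) criterion also stands unchanged, and should say how the nodular sentence relates to the change-in-character criterion, since no listed ground counts new nodular lesions as such. Section 6.2.3 and Section 3.6.1.7 must be reconciled; how the off-therapy rule should read is for the sponsor to decide.

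Then check the flowsheets of subjects with 8 or fewer total or nodular lesions at any time, and correct any PD, SD or PR call or progression date that depended on the literal reading. Report how many were affected, including if none.

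The cost is a few sentences and a limited review of existing records. The downside is that some progression dates may move earlier.

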6.3 TOXICITY CRITERIA

- The following adverse event management guidelines are intended to ensure the safety of each patient while on the study. Adverse events occurring during the study will be graded according to the NCI Common Terminology Criteria for Adverse Events version 4.0 (CTCAE v4.0) at:
http://ctep.info.nih.gov/protocolDevelopment/electronic_applications/ctc.htm
- Toxicity Attribution
 - The Principal Investigator or physician Associate Investigator will meet at least weekly to discuss adverse events, and document the relationship of the protocol intervention to each adverse event by assigning attribution per adverse event at time of clinical evaluation. Attribution will be rated as follows:
 - Unrelated: the adverse event is *clearly not* related to the investigational agents.
 - Unlikely related: the adverse event is *doubtfully* related to the investigational agents.
 - Possibly related: the adverse event *may be* related to the investigational agents.
 - Probably related: the adverse event is *likely* related to the investigational agents.
 - Definitely related: the adverse event is *clearly* related to the investigational agents

